1.0 Clinical Investigation Plan Overview

This study will be conducted as a prospective, nonrandomized, noncomparative, single-arm study enrolling a total of 50 patients at up to 30 global centers. The purpose of this study is to assess the safety and effectiveness of the Zenith® TX2® Low Profile Endovascular Graft in the treatment of patients with blunt thoracic aortic injury (BTAI).

A patient is deemed suitable for inclusion in the study if the patient has blunt thoracic aortic injury of the descending thoracic aorta and is suitable for treatment with the Zenith® TX2® Low Profile Endovascular Graft and 16 Fr, 18 Fr, or 20 Fr Z-Trak Plus® Introduction System. The study flow diagram is presented in Figure 1.

[figure not shown]

Figure 1. Study flow diagram

¹ Data collected prior to the patient’s signing of an Informed Consent are acceptable if they are standard of care at the investigative site.

2.0 Summary of Preliminary Investigations

2.1 Preclinical Testing

Non-clinical tests were conducted in accordance with Good Laboratory Practice requirements, or performed in compliance with verified methods and standard operating procedures to maintain the integrity of the results. *In vitro* testing has established reasonable safety of the device for the expected duration of the study and in the trial population to be studied. Please reference the Clinical Investigator Brochure for a summary of non-clinical testing.

2.2 Previous Clinical Experience

Please reference the Clinical Investigator Brochure for a complete description of the previous clinical experiences with the device or other similar devices, if applicable.

2.3 Justification for the Investigation

Endovascular repair has been reported as an independent predictor of survival for patients with blunt thoracic aortic injury (BTAI).¹ A meta-analysis performed by the Society for Vascular Surgery (SVS) showed a mortality rate of 9% with endovascular treatment as compared to 19% with open surgical repair. These findings led the SVS committee to preferentially recommend endovascular repair of traumatic thoracic aortic injuries over open surgical repair or nonoperative management.^{2,3}

However, limited endovascular treatment options are available for patients with blunt thoracic aortic injury. Furthermore, several publications have noted the need for devices with better arch conformability to accommodate the steep curvature of the aortic arch.^{3,4} Device infolding and collapse were also noted to be issues, often resulting from excessive oversizing at the site of fixation.^{3,4,5} As patients with BTAI are on average much younger⁶ than those treated for thoracic aortic diseases such as aneurysms,⁷ smaller diameter endovascular grafts with better arch conformability are needed to treat this patient population.

The Zenith[®] TX2[®] Low Profile Endovascular Graft has multiple design features that address the challenges of treating BTAI. The availability of the Zenith[®] TX2[®] Low Profile Endovascular Graft in smaller sizes and in smaller profile delivery systems will allow physicians to treat patients with smaller aortic anatomy and therefore eliminate the need to treat patients with larger endografts that are not suitable for their anatomy. Furthermore, the Zenith[®] TX2[®] Low Profile Endovascular Graft features a bare alignment stent in combination with a curved cannula on the introduction system to help ensure adequate proximal conformability. The Zenith[®] TX2[®] Low Profile Endovascular Graft device has been designed to accommodate a radius of curvature of 20 mm, whereas the currently available Zenith[®] TX2[®] TAA Endovascular Graft accommodates a radius of curvature of 35 mm. Based on these device design features and the clinical need for devices to treat BTAI, the clinical study to evaluate the safety and performance of the Zenith[®] TX2[®] Low Profile Endovascular Graft in patients with BTAI is justified.

3.0 Objectives of the Clinical Investigation

3.1 Primary Objectives

The objectives of the study are to evaluate the safety and effectiveness of the Zenith[®] TX2[®] Low Profile Endovascular Graft for the treatment of patients with BTAI. The primary safety endpoint will be all-cause and aortic-injury-related mortality (see Appendix C, Definitions) at 30 days. The primary effectiveness endpoint will be device success (see Appendix C, Definitions) at 30 days.

3.2 Secondary Objectives

Additional objectives for descriptive purposes include assessment of the following: procedural time and clinical utility measures at the intra-operative and post-procedure time points (see Appendix C, Definitions); major adverse events (see Appendix C, Definitions), injury healing (as determined by maximum transverse diameter at the site of injury), secondary interventions, endoleak, device migration, device patency, device integrity, and device collapse through the 5-year time point.

3.3 Specific Hypothesis to be Accepted or Rejected by Statistical Data

The primary and secondary endpoints of this study will be analyzed using only descriptive statistics, and will not be analyzed for the purpose of statistical inference.

4.0 Product Description and Intended Use

[figure not shown]
The Zenith® TX2® Low Profile Endovascular Graft is currently under clinical investigation for the treatment of patients with descending thoracic aortic aneurysms/ulcers. The treatment of BTAI uses the same proximal main body component as that intended for the treatment of aneurysms/ulcers. While the system that is available for the treatment of aneurysms/ulcers also has an overlapping distal component in order to provide the added coverage often needed, the available system for the treatment of BTAI will include only a proximal component, as the aortic segment requiring coverage is expected to be much more focal than that for an aneurysm/ulcer.

4.1 General Product Description

As depicted in Figure 2, the proximal component is constructed of self-expanding nitinol stents sewn to polyester graft material with braided polyester and monofilament polypropylene sutures. At the proximal end there is an uncovered stent and an internal sealing stent with fixation barbs that protrude through the graft material. All other stents are external to the graft material, except for the distal-most stent, which is located internal to the graft material. There are radiopaque markers at the proximal and distal edges of the graft. The proximal component will be available in multiple diameters and lengths and can be either straight or tapered, as shown in Table 1.

Proximal component (straight)

Proximal component (tapered)

Figure 2. Zenith® TX2® Low Profile Endovascular Graft proximal component

Table 1. Available Zenith® TX2® Low Profile Endovascular Grafts: diameter and length

Diameter (mm)*	Length of Straight Proximal Component (mm)	Length of Tapered Proximal Component (mm)
18	105	N/A
20	105	N/A
22	105	105
24	105	N/A
26	105	105
28	109	N/A
30	109	108
32	109	N/A
34	113	N/A
36	113	N/A
38	117	N/A
40	117	N/A
42	121	N/A
44	125	N/A
46	125	N/A

* For tapered components the proximal diameter is listed; taper is 4 mm

4.1.1 Delivery System

Each Zenith® TX2® Low Profile Endovascular Graft component will be shipped preloaded onto a 16 Fr, 18 Fr, or 20 Fr Z-Trak Plus® Introduction System (Figure 3), which has a sequential deployment method with built-in features to provide control of the endovascular graft throughout the deployment procedure. All delivery systems feature Flexor® introducer sheaths, which resist kinking and are hydrophilically coated, and use the Captor® Hemostatic Valve for added hemostasis. The proximal component is deployed from a delivery system

with a precurved inner cannula and a single trigger-wire release mechanism, which attaches the proximal and distal ends of the stent-graft to the delivery system following withdrawal of the sheath, until released by the operator.

[figure not shown]

Figure 3. Zenith® TX2® Low Profile Endovascular Graft proximal component Z-Trak Plus® Introduction System

4.2 Intended Use

The Zenith® TX2® Low Profile Endovascular Graft with the Z-Trak Plus® Introduction System is indicated for the endovascular treatment of patients with blunt thoracic aortic injury of the descending thoracic aorta having vascular morphology suitable for endovascular repair, including:

- Adequate iliac/femoral access compatible with the required delivery systems,
- Aortic segments (fixation sites) proximal and distal to the blunt thoracic aortic injury:
 - with a length of at least 20 mm and
 - with a diameter measured outer-wall to outer-wall of no greater than 42 mm and no less than 15 mm.

Please reference the Instructions for Use (IFU) for details regarding intended use.

4.3 Product Identification and Tracking

The identification and labeling of the products under investigation are outlined in the Clinical Investigator Brochure and Instructions for Use.

Products under investigation will be tracked throughout the course of the study through use of a Product Log, upon which lot numbers, quantity, and disposition of product will be recorded. Product Logs will be maintained by the sites. Additionally, the quantity(s), size(s), and lot number(s) of products used in patients will be recorded on the case report forms.

4.4 Instructions for Use

Please reference the manufacturer's Instructions for Use for complete instructions including implantation, storage and handling requirements, preparation for use, pre-use checks for safety and performance, and precautions to be taken after use.

4.5 Summary of Necessary Training and Experience

Please reference the manufacturer's Instructions for Use for a complete summary of the necessary training and experience required for use of this product.

4.6 Description of the Necessary Medical or Surgical Procedures

Please reference the manufacturer's Instructions for Use for a complete description of the procedures involved in the use of this product.

5.0 Design of the Clinical Investigation

5.1 Type of Investigation

The current investigation is a prospective, nonrandomized, noncomparative, single-arm clinical study. Enrollment is expected to be completed within 24 months of initiating the study.

5.2 Endpoints

The primary safety endpoint will be all-cause and aortic-injury-related mortality at 30 days.

The primary effectiveness endpoint will be device success, defined as technical success (i.e., successful access of the injury site and deployment of the Zenith® TX2® Low Profile Endovascular Graft in the intended location, and endovascular graft patency upon completion of deployment) with none of the following at 30 days:

- Device collapse;
- Type I or type III endoleak requiring reintervention; or
- Conversion to open surgical repair.

The secondary endpoints include an assessment of the following:

- At the intra-operative and post-procedure time points:
 - Procedural time and clinical utility measures (see Appendix C, Definitions);
- Through the 5-year time point:
 - Major adverse events (see Appendix C, Definitions),
 - Injury healing (as determined by maximum transverse diameter at the site of injury),
 - Secondary interventions,
 - Endoleak,
 - Device migration,
 - Device patency,
 - Device integrity, and
 - Device collapse.

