6.9 Follow-up

The results of the endovascular repair will be assessed by clinical and/or imaging evaluation intra-operatively and post-operatively, including within 7 days post-procedure, at 30 days (± 10 days) post-procedure, and at 6 months (180 ± 30 days), 12 months (365 ± 45 days), 2 years (730 ± 60 days), 3 years (1095 ± 60 days), 4 years (1460 ± 90 days), and 5 years (1825 ± 90 days) post-procedure as summarized in Table 2. Follow-up windows are intended as guidelines only. They are not absolute and are not intended to limit data collection due to scheduling conflicts.

Table 2. Study follow-up schedule

	Pre-op	Intra-op	Post-procedure	30-day	6-month	12-month ³
Clinical exam	X		X	X	X	X
Blood tests	X		X			
CTA	X ¹			X ²	X ²	X ²
Angiography		X				

¹The CTA must be obtained as close as possible to the study procedure.

²MR or non-contrast CT imaging may be used for those patients experiencing renal failure or who are otherwise unable to undergo contrast-enhanced CT scan, with TEE being an additional option in the event of suboptimal MR imaging.

³Performed yearly for 5 years.

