7.4 Missing Data

Missing data will be addressed using three primary strategies: 1) estimating missing data with the best available data, 2) case deletion, and 3) multiple imputation.

The first strategy may be used for missing imaging data. Previous clinical trial experience suggests that some portion of the imaging data may not meet the criteria for accurate measurements by the core laboratory. However, it is recognized that the investigator uses

this information to provide the best possible care for the patient. Therefore, it is reasonable to substitute any missing core laboratory measurements with the corresponding measurements made by the investigator (or his/her staff). In addition, the absence or presence of clinical sequelae may provide the required missing core laboratory assessment of device performance. Furthermore, imaging at subsequent time points may be available, making it possible to infer patient status at the time point of interest. This strategy is a best approximation of the missing data value.

The second strategy is case deletion. If the amount of missing data does not result in a reduction of analyzable patients to a number that is below that required for sufficient statistical power of the primary endpoints, then case deletion will be the method of choice for that analysis.

The third strategy is multiple imputation. This method will be used to predict missing endpoint data. For missing primary endpoint data, the multiple imputation technique will be used to generate random Bernoulli observations with probabilities equivalent to the proportion of (non-missing) “Yes”/ “No” entries. It is anticipated that no covariates will be used for this model. This model-based imputation exercise may provide estimates of the missing data that can be utilized in estimating event rates and confidence bounds. Strategies originating from Schafer¹⁵ will be used, supplemented with notes provided by Schafer.¹⁶ The computations will be performed using PROC MI and PROC MIANALYZE in SAS version 9.1 or later. Unless evidence suggests otherwise, missing at random data will be assumed.

Additional analyses of missing data may be performed as appropriate, including a tipping point analysis.

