Stroke:	Permanent clinically significant central nervous system deficit.
Success, Device (30-day):	Technical success, with none of the following at 30 days: 
• Device collapse;• Type I or type III endoleak requiring reintervention; or• Conversion to open surgical repair.
Success, Technical:	Successful access of the injury site and deployment of the Zenith® TX2® Low Profile Endovascular Graft in the intended location. The endovascular graft must be patent at the time of deployment completion as evidenced by angiographic imaging.

- Tortuosity: Fixation zone and iliac artery tortuosity will be graded based upon the following:
None: Lack of tortuosity;
Mild: Fairly straight arteries;
Moderate: Angulation manageable with stiff wires, < 70 degrees;
Severe: Angulation difficult, may require surgical exposure for straightening, not straightened entirely with wires; or
Prohibitive: Severe and cannot be resolved in the opinion of the investigator.
- Traumatic Aortic Injury: Injury will be graded based upon the following^{8,17}:
Grade 1: Intimal tear;
Grade 2: Intramural hematoma/large intimal flap (LIF);
Grade 3: Pseudoaneurysm; or
Grade 4: Rupture.

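### Does device success need a rule for patients who die before 30-day imaging, and should graft infolding be an endpoint?

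*Combined protocol and SAP*

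**What the plan says.** Device success is defined twice with the same content. Section 5.2: "The primary effectiveness endpoint will be device success, defined as technical success", followed by three disqualifying events. Appendix C: "Technical success, with none of the following at 30 days", with the same three: device collapse, type I or III endoleak requiring reintervention, and conversion to open repair. Death is not among them. It is counted elsewhere in 5.2: "The primary safety endpoint will be all-cause and aortic-injury-related mortality at 30 days". It is also a major adverse event (Appendix C).

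Section 6.9 plans assessment "within 7 days post-procedure, at 30 days (± 10 days) post-procedure" and later. Table 2 marks a clinical exam and blood tests at the post-procedure visit, and the first post-operative CTA at the 30-day visit. Follow-up ends at death; autopsy may be requested (6.10).

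Section 7.4 gives three general strategies for missing data and does not mention death:
- Best available data: "the absence or presence of clinical sequelae may provide the required missing core laboratory assessment of device performance".
- If enough patients remain, "then case deletion will be the method of choice for that analysis".
- Multiple imputation from the observed proportion, without covariates. "Unless evidence suggests otherwise, missing at random data will be assumed".

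A tipping point analysis is optional. Section 5.6 puts every patient whose procedure has begun in the intent-to-treat population. Sections 3.3 and 7.2 make all endpoints descriptive.

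On infolding, 2.3 names it with collapse as a known problem and Appendix C defines it separately from collapse. No endpoint in 3.2 or 5.2 names it. Section 5.3 item 1 collects deployment issues.

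**The concern.** A patient who dies on day 5 with a deployed, patent graft will normally have no scheduled CT evidence on collapse or endoleak. The plan then appears to leave three outcomes open: success (no listed event was recorded), removal from the denominator, or a value drawn at the rate of the other patients. None of these counts an aortic-related death against the device by default. Deletion also sits badly with the intent-to-treat population of 5.6. If many patients died early, the primary effectiveness rate could depend on a choice made after the data were seen, and a reader might take a high rate as reassurance about patients who died of their aortic injury.

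The infolding point looks similar. Section 2.3 presents infolding and collapse together as weaknesses of existing devices, yet only collapse is an endpoint. An infolded graft that stays patent and causes nothing further would still be a device success.

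**Working it through.** **Inputs.** Expected 30-day mortality is 7.6%, with a stated need for 43 patients and enrolment of 50 (7.1). Appendix E gives 80 rows of patients and deaths. Success in survivors, *s*, is not given in the documents. I assume 95% and show 90% and 100%.

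**The plan's own figures.** Appendix E sums to 112 deaths in 1477 patients: 112/1477 = 7.58%, which is the stated 7.6%. The sample size is 1.96² × 0.076 × 0.924 / 0.08² = 42.15, rounded up to 43. Both reproduce.

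**How many deaths.** Expected: 50 × 0.076 = 3.8. With X ~ Binomial(50, 0.076), P(2 ≤ X ≤ 6) = 0.917 − 0.098 = 0.819. These are upper figures for deaths without imaging, because some patients may be scanned before they die.

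**What the routes give.** Let *d* patients die, each with technical success and no listed event.
- Deaths scored as success: (s(50 − d) + d)/50.
- Deaths deleted, or imputed at the observed rate (expected value): s.
- Gap: d(1 − s)/50.

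| s | d | Deaths as success | Deleted or imputed | Gap (points) |
|---|---|---|---|---|
| 95% | 2 | 95.2% | 95.0% | 0.2 |
| 95% | 4 | 95.4% | 95.0% | 0.4 |
| 95% | 6 | 95.6% | 95.0% | 0.6 |
| 90% | 2 | 90.4% | 90.0% | 0.4 |
| 90% | 4 | 90.8% | 90.0% | 0.8 |
| 90% | 6 | 91.2% | 90.0% | 1.2 |
| 100% | any | 100% | 100% | 0 |

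One patient in 50 is 2 points, so every gap is smaller than one patient. In whole patients, with 4 deaths and 2 survivor failures, the results are 48/50 = 96.0% (exact 95% interval 86.3 to 99.5%) and 44/46 = 95.7% (85.2 to 99.5%). The 0.3-point difference is negligible beside intervals more than 13 points wide.

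**Inference from sequelae.** This is the one permitted route that can lower the rate. Each death judged from clinical evidence to involve a listed failure takes off 1/50, or 2 points. With 4 deaths and s = 95%, one such death gives (43.7 + 4 − 1)/50 = 93.4%. This reflects evidence about the device, so it is not an arbitrary scoring choice.

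**Counting deaths as failures.** If every death failed, s = 95% gives 45.6/50 = 91.2%, 43.7/50 = 87.4% and 41.8/50 = 83.6% for 2, 4 and 6 deaths. These falls come from a different endpoint, one combining survival with device function. They do not measure ambiguity in the plan's endpoint.

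**Which 7.4 route would apply.** Section 7.4 makes deletion conditional on keeping enough patients but gives no number. If that number is the 43 of 7.1 (my assumption), 50 − 43 = 7 deletions are possible. P(X ≤ 7) = 0.966, so on deaths alone imputation would seldom be reached.

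**Infolding.** No rate is given, so only the unit effect can be stated: 2 points per case if it were scored as a failure. Appendix C defines it as occurring at deployment. Deployment issues are recorded (5.3), angiography is done during the procedure (Table 2), and procedural imaging goes to the core laboratory (10.2). Infolding that led to lost patency, endoleak, secondary intervention or conversion would appear under those outcomes. Its absence from the 5.3 list proves little, because 5.3 does not list collapse either, and collapse is part of the primary endpoint.

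**The case for a change.** The strongest case for a change is that, in a descriptive single-arm study, the reported rate and its denominator are the result. Section 5.4 promises uniform endpoint definitions and a prospective analysis plan, and 7.5 expects the data to inform later device variants, so an unclear denominator could carry forward. A fatal rupture of the injured aorta is the hardest example. It would be adjudicated as aortic-injury-related death, yet rupture is not on the device-success failure list. Unless a listed event is inferred from sequelae, that patient is a success, deleted or imputed. The mortality endpoint does not show how deaths entered device success, and the analysis that would is optional.

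What stands: the text has no rule specific to death, and deletion does not fit 5.6. Inference from sequelae also needs judgement and can move the rate by 2 points per death.

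What does not stand is that the result is therefore unsound. The definition is the absence of listed events, and it already yields an answer. Endoleak requiring reintervention and conversion depend on clinical acts that are recorded without a 30-day scan; collapse is the component that depends most on later imaging. Deaths after failed access, failed deployment, lost patency at completion or conversion already fail. Aortic-injury-related death includes any death caused by the implant procedure, which need not mean the device failed, so keeping survival and device function apart is a legitimate choice. The clinical events committee adjudicates reported events, and aortic-injury-related deaths appear beside device success in the other primary endpoint. A reader can see how many patients died and can compute the all-deaths-as-failures figure if the report shows outcomes by patient.

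**Conclusion.** No change follows. The definition lacks a sentence on early deaths, and an analyst can fill that gap sensibly with what the plan already holds: the event-based definition, the intent-to-treat population of 5.6 and the best-available-data strategy of 7.4. Scoring early deaths as successes differs from deleting or imputing them by 0.2 to 0.6 points with 2 to 6 deaths and 95% survivor success, by at most 1.2 points at 90%, and by nothing at 100%. A death judged a device failure from sequelae moves the rate by 2 points, as it should. The falls to as low as 83.6% arise only if deaths are made failures, which the endpoint deliberately does not do. Mortality is reported beside device success and no hypothesis is tested.

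Naming infolding as an endpoint, or scoring infolding without consequences as a failure, is a preference with no rate behind it; the plan already has places where it would be recorded.

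This rests on the 7.6% mortality of 7.1, the assumed survivor success rates, and the assumption that the deaths at issue have technical success and no listed event. The number of deaths without any imaging is unknown. The case report form is not in the documents, so how infolding is recorded cannot be confirmed.

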5.3 Variables to be Measured to Demonstrate Achievement of Endpoints

To evaluate deployment characteristics, procedural outcome, and follow-up, the following data points will be collected:

- 1) Assessment of system performance including: deployment issues, ease of insertion, visualization, and ease of removal;
- 2) Clinical utility measures such as days to discharge from hospital;
- 3) Complications including major adverse events during procedure and at follow-up;
- 4) Device integrity findings at completion of procedure and follow-up: device migration, patency, stent fracture, and graft kinks;
- 5) Type and sources of endoleaks at procedure and follow-up; and
- 6) Secondary interventions performed.

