5.5.1 Inclusion Criteria

All patients must meet all of the following inclusion criteria to be eligible for enrollment into this study:

- 1) Blunt thoracic aortic injury of the descending thoracic aorta
- 2) Suitable for treatment with the Zenith® TX2® Low Profile Endovascular Graft and 16 Fr, 18 Fr, or 20 Fr Z-Trak Plus® Introduction System
- 3) Treatment with the Zenith® TX2® Low Profile Endovascular Graft can be performed within 14 days of the blunt thoracic aortic injury
- 4) Age \geq 16 years
- 5) Proximal fixation site length measuring \geq 20 mm between the left common carotid artery and most proximal extent of the injury site (covering left subclavian artery is acceptable)
- 6) Distal fixation site length measuring \geq 20 mm between the distal-most aspect of aortic injury and most distal extent of graft
- 7) No previous placement of a thoracic endovascular graft
- 8) No prior open surgical repair involving the descending thoracic aorta including suprarenal aorta and/or arch
- 9) Proximal neck diameter, measured outer-wall to outer-wall on a sectional image or multiplanar reconstruction (CT), \geq 15 mm and \leq 42 mm
- 10) Distal neck diameter, measured outer-wall to outer-wall on a sectional image or multiplanar reconstruction (CT), \geq 15 mm and \leq 42 mm
- 11) Ability to preserve the left common carotid artery and celiac artery
- 12) Willing and able to comply with the follow-up schedule

- 13) Informed consent given by the patient or a legally authorized representative [Note: For pediatric patients, in addition to obtaining permission from their parents or guardians, assent from the patients may need to be obtained based on IRB requirements. See Section 6.2 for further information.]

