7.2 Performance Goals

The primary and secondary endpoints of this study will be analyzed using only descriptive statistics, and will not be analyzed for the purpose of statistical inference, as these patients

typically have extensive concomitant injuries that would confound the interpretation of statistical comparisons to alternative treatments.

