7.3 Site-level Poolability

Poolability of data from multiple sites will be verified by examining the primary and secondary safety and effectiveness measures among sites as well as important patient baseline characteristics. Site-level poolability will be considered appropriate provided that these measures are similar among sites.

It is expected that many sites will have too few patients to provide reasonable site-level estimates of primary, secondary, and baseline measures. Each investigative site will be allowed to enroll no more than 10 patients (20% of the total enrollment) to ensure the overall result is not biased by the results from a single site. Pooling of this information will be explored based on hospital size (large versus small), site enrollment (large versus small), type of hospital (community versus teaching), and other group-wise strategies.

It is recognized that patient baseline characteristics may differ among sites, with some sites routinely treating patients with more severe aortic injuries. It is anticipated that the primary and secondary endpoint measures may be related to covariates that reflect this severity, which are in turn related to outcome. Thus, any observed site-specific differences among the primary or secondary endpoints will be checked for confounding with other measured covariates. This can be accomplished using regression models (linear and logistic where appropriate) that include site and other measured covariates as independent variables.

Should one or more sites significantly differ from the rest, then all subsequent analyses will include the discriminating covariate or a covariate to distinguish between the unusual site(s) and those sites that are considered poolable.

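### Injury healing is read only from maximum transverse diameter, although eligible grade 2 injuries need not enlarge the aorta; diameter should be reported by grade and flap or hematoma resolution recorded

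*Combined protocol and SAP*

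**What the plan says.** Section 5.2 sets the secondary endpoint through 5 years as "Injury healing (as determined by maximum transverse diameter at the site of injury"), and section 3.2 uses the same words for the descriptive objective. Appendix C has no entry for healing. Neither section names a baseline scan, a direction or amount of change, or whether the diameter runs to the inner or the outer wall.

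Entry is broad. The first inclusion criterion in section 5.5.1 is "Blunt thoracic aortic injury of the descending thoracic aorta", with no requirement that the aorta be enlarged. Section 5.5.2 removes grade 1 only. Appendix C then lists "Grade 2: Intramural hematoma/large intimal flap (LIF") and, as a distinct grade, "Grade 3: Pseudoaneurysm; or", followed by rupture as grade 4.

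On analysis, section 7.2 limits the endpoints to description and rules out inference: "The primary and secondary endpoints of this study will be analyzed using only descriptive statistics, and will not be analyzed for the purpose of statistical" … No tabulation by injury grade is mentioned. Severity of the aortic injury appears only in section 7.3, as a possible explanation of differences between sites.

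**The concern.** A healing measure should read differently when the injury has gone and when it has not. Diameter plausibly does so where the injury widens the aorta. A large intimal flap is a lesion of the inner lining, and nothing in its definition implies a wider vessel. It could resolve or persist at the same maximum diameter, and the endpoint would then give the same reading for both.

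Two consequences follow. For grade 2 patients, the stated objective of assessing healing may go unanswered however complete the follow-up is, because the fault lies in what is measured and not in how much is collected. Across all patients, a summary that ignores grade would mix patients in whom diameter carries information on healing with patients in whom it may not, so its value would depend partly on how many of each were enrolled. Since description is this study's only output, what each reported number means matters more here than it would beside a formal test. Section 7.5 also expects the effectiveness data to serve as prior information for later device variations.

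**Working it through.** The plan gives no figure for injury healing, so there is none to reproduce. Its sample size of 43 (section 7.1) is built from the 30-day mortality rate (7.6%) and a margin of 8% alone; healing does not enter it. The check is therefore of the text.

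**1. Is diameter the only healing criterion?** Yes. Sections 3.2 and 5.2 use the same parenthesis, and Appendix C adds nothing. Section 5.3, which lists the data to be collected, comes closest with "Device integrity findings at completion of procedure and follow-up: device migration, patency, stent fracture, and graft kinks"; none of its six items names injury diameter, flap resolution or hematoma resolution.

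**2. Are injuries without enlargement eligible?** Yes, as far as the criteria go. Only grade 1 is excluded, no inclusion criterion concerns diameter at the injury itself, and the diameter limits (15 to 42 mm) apply to the proximal and distal necks.

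**3. Is the diameter specified well enough to be informative in grade 2?** Compare it with other measurements in the same plan:

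| Measurement | Wall convention | Reference scan | Threshold |
|---|---|---|---|
| Neck diameter (5.5.1) | outer to outer | pre-operative CT | 15 to 42 mm |
| Access vessel diameter (5.5.2) | inner to inner | sectional image | suited to sheath size |
| Radiographic migration (Appendix C) | not applicable | first post-operative CT | more than 10 mm |
| Injury healing (3.2, 5.2) | not stated | not stated | not stated |

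The missing wall convention matters for intramural hematoma. Blood within the wall may alter an outer-wall diameter, a luminal diameter, or both to different degrees. The plan does not say which is read.

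**4. What does a summary over all grades show?** Let w2, w3 and w4 be the shares of each grade and d2, d3 and d4 the mean changes in diameter. The overall mean change is w2·d2 + w3·d3 + w4·d4. If the grade 2 patients include flaps that do not enlarge the aorta, those flaps contribute zero change whether they resolve or persist. Two consequences hold for any shares: the overall mean does not move with the fate of those flaps, and it does move with w2 when healing within each grade stays the same. The documents give none of the shares or mean changes, so no numerical effect can be calculated.

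**5. Can the grade mix vary?** The plan expects it to. Section 7.3 anticipates sites that differ in baseline, "with some sites routinely treating patients with more severe aortic injuries".

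**6. Are the scans available?** Yes. Table 2 schedules CTA before the procedure, at 30 days, at 6 and 12 months, and yearly to 5 years. Sections 5.4 and 10.2 provide for core-laboratory reading. Footnote 2 of Table 2 allows MR or non-contrast CT at follow-up for patients who cannot have contrast, so some follow-up scans may not show a flap.

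**The case against.** The strongest reply is that the central premise is an inference. Appendix C gives labels for the grades and does not say how diameter behaves in any of them. This stands: that grade 2 need not enlarge the aorta is read from the definitions, and that results will be summarized across grades is read from the absence of any breakdown.

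A second reply is that other evidence of treatment failure is collected. Endoleak, secondary interventions and aortic-injury-related mortality are recorded separately, and section 7.3 commits to checking site differences for confounding by severity. This also stands, and it limits the harm. But continuing flow into the injury is not the same as persistence of a flap or hematoma, and a check of site differences does not supply a healing criterion for grade 2.

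A reader might go further in three directions that the documents do not support.
- **Diameter cannot show healing in any grade 2 patient.** This is too strong, because an intramural hematoma may change an outer-wall diameter. The argument is strongest for flaps, whose share of grade 2 is unknown.
- **Graft oversizing hides healing.** The ratios that can be formed are 18/15 − 1 = 20% at the smallest permitted neck and 46/42 − 1 = 9.5% at the largest. Both use fixation-site limits, not the injury site. The second is a maximum, since 46 mm is the largest graft, and sizing rules are left to the Instructions for Use.
- **Diameter fails for grade 4 as well.** Nothing in the documents says how diameter behaves after a rupture is covered.

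**Conclusion.** The concern holds in a limited form. As written, the endpoint may not distinguish a healed from a persistent injury in grade 2 patients, particularly those with a large intimal flap, and an overall summary would partly reflect the grade mix. This rests on two assumptions: that some grade 2 injuries leave the maximum diameter unchanged, and that no breakdown by grade is intended.

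The size is unknown. A reader might wish to put a ceiling on the proportion of patients who could show a decrease. The plan defines no such proportion, and any ceiling would only restate an assumed grade 2 share. Mortality, device success and the sample size do not depend on this endpoint. The change is worth making because it is cheap and improves what the study can say about healing; it is not a condition for the study to be valid.

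**What to change.** In sections 3.2 and 5.2, with a matching entry in Appendix C and an added item in section 5.3:

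- Keep maximum transverse diameter for all patients. Name the pre-procedure CTA as baseline and state one wall convention for every time point.
- Tabulate change in diameter by injury grade (2, 3 and 4) alongside the overall summary, with the number of patients in each grade.
- For grade 2, add a core-laboratory field for resolution of the flap or hematoma on the scheduled CTAs: resolved, persistent, or not assessable. The last category is for imaging that does not allow the reading, such as non-contrast CT, and should not be counted as either of the other two.

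The cost is protocol and SAP wording and one extra field on the core-laboratory form, read from scans already planned. There is no new imaging and no change in enrollment. The drawback is that 50 patients split over three grades leaves small groups, so the results by grade will be imprecise and should be presented as counts and simple summaries.
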